#### The proportion of patients with a Bathel score ≥ 95 points at 90±7 days

The proportion of patients with a Bathel score ≥ 95 points at 90 days in treatment groups will be compared by Chi-squared tests. This will also be tested by logistic regression model. The odds

ratio with 95% CI will be reported.

#### 13. Safety Analyses

All analyses of safety data will be carried out using the safety set (SS) population.

#### **Bleeding Events**

The incidence of symptomatic intracranial hemorrhage within 36 hours (as defined by ECASS III criteria);

The incidence of symptomatic intracranial hemorrhage within 90 days (as defined by ECASS III criteria);

The incidence of PH2 intracranial hemorrhage within 36 hours (according to SITS criteria);

The incidence of any intracranial hemorrhage within 90 days;

The incidence of other significant hemorrhage events within 90 days (as defined by GUSTO criteria).

For most bleeding events, the number of bleeding events occurring over the treatment period will be summarized and Chi-squared test or Fisher's Exact test will be used to compare the number of bleeding events between treatment groups. This will also be tested by logistic regression model. The odds ratio with 95% CI will be reported.

#### **Adverse Events**

Adverse events (AEs) will be coded using the MedDRA coding dictionary (Version 6.0 or a later release) and grouped by system organ class (as detailed in the study protocol). Separate data display listings and summaries will be presented for adverse events that start prior to first dose of study medication (pre-treatment), whilst on study medication (during treatment) and after the last dose of study medication (post-treatment).

Within each treatment group, the number and percentage of patients experiencing an AE will be summarized by system organ class and preferred term and Chi-squared test or Fisher's Exact test will be used to compare the number of each grouped AE event between treatment groups. In addition, a separate summary will be provided for AEs experienced by more than 5% of patients in either of the treatment groups.

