#### 5.3 Method of administration

#### Treatment group (rhTNK-TPA 0.25mg/kg, 25mg at most):

RhTNK-TPA 0.25mg/kg: Each vial is dissolved in 3ml of sterile water for injection to obtain a solution with a concentration of 5.33mg/ml. The amount required for medication is calculated and measured according to the actual body weight of the

subject, 25mg at most. The solution is administered via single intravenous bolus injection in 5-10 seconds.

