#### Control group (rt-PA 0.9mg/kg):

RT-PA 0.9mg/kg: The product is dissolved in sterile water for injection to obtain a solution with a concentration of 1mg/ ml. The amount required for medication is calculated and measured according to the actual body weight of the subject. 10% of the solution is injected by intravenous bolus, and the remaining 90% is injected by intravenous drip within 1h.

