### 6.3 Medication compliance

In the recruitment and screening stage, the purpose of the trial, the basic information of the study drugs, the protocol, the trial process, the administration regimens, clinical observation, the potential risk if participating in the study, compensation, etc., will be introduced in detail, so that subjects could be fully informed and voluntarily participate in the study to improve the compliance of the study. This study uses single dose, to be administered by the study nurse. Before administration, subject number, administration table and dosage should be carefully checked; after administration, the remaining quantity of study drugs, empty packages and administration equipment should be carefully checked.

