## 9.1.2 Recording of adverse events

Adverse event reporting period: adverse event recording starts immediately after the subjects receive the study drug, until the last follow-up after completion of the study. All AE findings must be recorded by the investigator (or designee) in the AE section of the eCRF. The record includes a description of the AE, the time of occurrence and resolution, severity, relationship with the study drugs, measures taken, and outcomes.

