#### 5. Design

This study will evaluate the efficacy and safety of rhTNK-tPA (0.25 mg/kg) compared with standard rt-PA (0.9mg/kg) in the treatment of hyperacute ischemic stroke (within 4.5 h of symptom onset). This is a multicenter, prospective, centrally randomized, open label, blinded-endpoint, parallel active controlled, non-inferior phase III clinical trial.

The drug administration method of the test drug (rhTNK-TPA) is as follows: according to the

body weight of the patients, the final dose is determined at 0.25mg/kg; Each vial is dissolved in 3ml of sterile water for injection to obtain a solution with a concentration of 5.33mg/ml. The amount required for medication is calculated and measured according to the actual body weight of the patient, 25mg at most. The solution is administered via single intravenous bolus injection in 5-10 seconds.

The administration method of active control drug (rt-PA) is as follows: The dose required for medication is calculated and measured according to the actual body weight of the patient based on a standard of 0.9 mg rt-PA/kg. The 10% of the dose is injected by intravenous bolus, and the remaining 90% is injected by intravenous drip within 1h.

The target population of this study is patients with critical hyperacute ischemic stroke (within 4.5 h of symptom onset), for whom considering the benefit of patients, intravenous thrombolytic therapy should be given as soon as possible after the onset, in order to achieve vascular recanalization or reperfusion and obtain a better prognosis. Due to the different administration methods of test drug and active control drug, and the inconvenience of the double-blind double-dummy design which may delay treatment and is not conducive to the benefit of patients. Therefore, this study adopts the form of open-label trial. To minimize bias, all endpoints will be evaluated in a blind manner by a qualified study physician.

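### The SAP's adverse event tables by treatment phase cannot be compared between arms, because time on drug is seconds for rhTNK-tPA and up to about an hour for alteplase

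*Supplement*

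**What the plan says.** The Adverse Events paragraph of section 13 in the final SAP divides AEs by when they start relative to dosing. The first class is set out as follows: "Separate data display listings and summaries will be presented for adverse events that start prior to first dose of study medication (pre-treatment"). The other two are "whilst on study medication (during treatment) and after the last dose of study medication (post-treatment"). No length in minutes, hours or days is attached to any class.

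Protocol V2.2, section 5.3, gives the dosing. For rhTNK-tPA: "The solution is administered via single intravenous bolus injection in 5-10 seconds". For alteplase: "10% of the solution is injected by intravenous bolus, and the remaining 90% is injected by intravenous drip within 1h". Section 5 of the SAP repeats both. Section 6.3 of the protocol confirms that there is no later dosing: "This study uses single dose, to be administered by the study nurse".

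On collection of AEs, protocol section 9.1.2 says that "adverse event recording starts immediately after the subjects receive the study drug, until the last follow-up after completion of the study". Section 9.1.1 likewise defines an AE as something that happens after study drug has been received.

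The next paragraph of the SAP's Adverse Events text asks for a summary by system organ class and preferred term, with a chi-squared or Fisher comparison between arms. That paragraph does not mention phase.

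**The concern.** A split into before, during and after treatment suits a trial in which both arms take drug over a similar span. Here the arms differ by design in how long the drug takes to deliver. A class defined by being on drug therefore measures delivery time as much as safety.

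The events affected are those of the first hour, such as early bleeding, allergic reactions and blood pressure changes. A reader interested in acute safety would turn to a during-treatment table for exactly these. On rhTNK-tPA that table will be almost empty whatever the drug does. On alteplase it will hold the infusion-hour events, which sites are told to record (protocol sections 6.1 and 7.3). Seen side by side, the two columns invite a comparison that they cannot support.

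The pre-treatment class is a separate, smaller inconsistency. The SAP asks for a table for which the protocol collects no data.

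**Working it through.** The plan states no figure for this point, so there is nothing of its own to reproduce. The check compares the windows and then illustrates their effect.

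**1. Length of the during-treatment window**

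- rhTNK-tPA: 5 to 10 s (protocol 5.3; SAP section 5).
- Alteplase: up to 1 h = 3600 s (same sections).
- Ratio: 3600/10 = 360 to 3600/5 = 720.
- The drip time is an upper limit. If a drip took 30 minutes, the ratio would be 1800/10 = 180 to 1800/5 = 360.

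Dosing happens once, so no later time on drug evens this out.

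**2. How one event is classed**

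| AE start, from start of dosing | rhTNK-tPA | alteplase (1 h drip) |
|---|---|---|
| 5 seconds or less | during | during |
| 30 minutes | post | during |
| 2 hours | post | post |

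Only events that start after the bolus and within roughly the first hour are classed differently.

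**3. Illustration of size**

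The documents give no first-hour AE risk. Let q be that risk, assumed equal in both arms and spread evenly over the hour (constant hazard). Take 715 patients per arm (SAP section 6), the longer 10 s bolus, and a 1 h drip. The expected number of patients with an event starting in a window of t seconds is

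715 × [1 − (1 − q)^(t/3600)].

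For alteplase, t = 3600 and this is 715 × q. For rhTNK-tPA, t = 10.

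| Assumed q | alteplase, during | rhTNK-tPA, during |
|---|---|---|
| 0.5% | 715 × 0.005 = 3.6 | 0.01 |
| 1% | 715 × 0.01 = 7.2 | 0.02 |
| 2% | 715 × 0.02 = 14.3 | 0.04 |
| 5% | 715 × 0.05 = 35.8 | 0.10 |

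The true difference between arms is nil in every row. The events missing from the rhTNK-tPA during-treatment table reappear in its post-treatment table. At q = 2%, for example, 14.3 − 0.04 ≈ 14.3 patients move there.

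**4. The pre-treatment class**

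Set side by side, SAP section 13 asks for AEs starting before the first dose, while protocol 9.1.1 and 9.1.2 make such an event neither an AE nor recordable as one. Taken at its word, the protocol leaves that table empty.

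**5. What is not touched**

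- Symptomatic haemorrhage and PH2 within 36 hours, and symptomatic haemorrhage, any intracranial haemorrhage, other significant bleeding, mortality and AE/SAE incidence within 90 days (SAP section 3) all run on clocks common to both arms.
- Protocol 12.5 calculates AE incidence on the safety set without phases.
- The SAP's bleeding and death paragraphs speak loosely of a treatment period. The endpoint definitions carry the 36-hour and 90-day limits, and I take those as governing.

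**The case against.** The strongest reply is that this is a supplementary display. The SAP asks only for listings and summaries by phase. All events appear in one table or another, and the routes of administration are stated so plainly that an empty during-treatment column for a bolus explains itself. All of this stands, and it limits the weight of the point.

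A second reply is that clock time is itself an assumption. Elsewhere the SAP works in days: the full analysis set refers to one-day treatment, and protocol violations are dated from the treatment start date. If AE phases were assigned by calendar date, dosing would normally fall on the same day in both arms and most of the asymmetry would vanish. This is possible, but the SAP does not say so for AEs. Its boundary is the last dose, not the day of dosing, and protocol 9.1.2 records the time of occurrence.

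Two stronger readings are tempting, and the documents support neither.

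- A reader might infer that the split will produce false significant differences. A Fisher test on 0 against 14 of 715 does give p = 0.0001. But the SAP attaches its test to the organ-class and preferred-term summary and nowhere says it is run by phase. The p-value also depends wholly on the assumed risk: 0 against 4, from q = 0.5%, gives p = 0.12.
- A reader might infer that the trial's safety conclusions are biased towards rhTNK-tPA. The during-treatment table would look favourable to it, but the same events sit in its post-treatment table, which is also presented, and the safety endpoints use common windows.

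**Conclusion.** The point holds as a limited reporting fault. The SAP states a rule that, read by clock time, classes the same first-hour AE differently by arm, and nothing in the protocol or SAP aligns the phases. The phase summaries therefore cannot be compared between arms. The pre-treatment class contradicts the protocol's AE definition and recording period.

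The during-treatment window is 360 to 720 times longer on alteplase for a full one-hour drip. In patients, the size is unknown. Under an equal assumed first-hour risk of 0.5% to 2% and 715 per arm, the during-treatment tables would differ by about 4 to 14 patients with no real difference between the drugs. This rests on clock-time assignment, a drip close to one hour, and a constant hazard over that hour.

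The prespecified haemorrhage, mortality and overall AE/SAE comparisons stand. The change is worth making because it is nearly free, not because a main conclusion is at risk.

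**What to change.** In the Adverse Events paragraph of SAP section 13:

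- Replace the three phases with non-overlapping windows counted from the start of study drug and identical in both arms, for example 0-24 h, after 24 h to day 7, and after day 7 to day 90. Keep the overall 90-day table.
- Drop the pre-treatment AE class, or list conditions that begin before dosing as medical history.
- If events during the alteplase infusion are still to be listed, label that listing descriptive and not for comparison between arms.
- State which summaries carry the chi-squared or Fisher comparison.

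The cost is SAP wording and one derived variable, time from start of study drug to AE onset. Both inputs are already called for: AE time of occurrence in protocol 9.1.2, and thrombolysis times in 6.1 and 7.3. If the case report form holds only the date of onset, the windows should be set in days. No new data and no change to patient care are needed.

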#### **Deaths and Serious Adverse Events**

Summary tables and data displays will be provided for serious adverse events (as detailed in the study protocol). In addition, all deaths and serious AE's will be documented in a case narrative format in the clinical study report.

The number of deaths occurring over the treatment period will be summarized and Chi-squared test or Fisher's Exact test will be used to compare the number of deaths between treatment groups.

#### Changes in the statistical analysis plan

#### SAP version 1.0

#### 6. Sample size estimates

According to a paper published in the Lancet in 2014 about meta-analysis of the incidence of 90-day MRS score of 0-1 (treatment within 4.5h) regarding rt-PA versus Placebo, the data under age of 80 was collected with the incidence of rt-PA and Placebo in clinical trials initiated by European researchers, of which the meta-analysis result of RR and 95% confidence interval were 1.24 and 1.14-1.36, respectively. According to the Guidelines for the Design of Non-inferiority Drug Clinical Trials, the lower 95% confidence interval of the Meta analysis should be used to calculate the non-inferiority threshold given that the primary endpoint is a high priority index. Therefore, based on the lower CI limit of 1.14, together with a efficacy of 25% of the active control, the non-inferior threshold was determined as 0.906. Then assuming  $\alpha = 0.025$ using one-sided test, power 1- $\beta$ =0.8, treatment group (TNK) incidence of 64%, control group (rt-PA) incidence of 63%, real RR= 1.02, the sample size was calculated by PASS software to be 643 cases in each group;

#### Changes in SAP version 1.3

#### 6. Sample size estimates

According to a paper published in the Lancet [1] in 2014 about meta-analysis of the proportion of 90-day mRS score of 0-1 (treatment within 4.5h) regarding rt-PA versus Placebo, the RR and 95% confidence interval 1.24 1.14-1.36, respectively. were and According to the Guidelines for the Design of Non-inferiority Drug Clinical Trials [2], the lower 95% confidence interval of the Meta analysis should be used to calculate the non-inferiority threshold given that the primary endpoint is a high priority index. Therefore, based on the lower CI limit of 1.14, together with an efficacy of 50% of the active control, the non-inferior threshold was determined as 0.937. Then assuming  $\alpha$ =0.025 using one-sided test, power 1-β=0.85, treatment group (TNK) incidence of 63.64%, control group (rt-PA) incidence of 59.32%, RR= 1.07, the sample size was calculated to be 642 cases in each group; considering a dropout rate of 10%, the sample size was determined as 715 cases in each group and the total sample size is estimated to be 1430 cases.

\*Then assuming  $\alpha$ =0.025 using one-sided test, power 1- $\beta$ =0.85, treatment group (TNK) incidence of

considering a dropout rate of 10%, the sample size was determined as 715 cases in each group, a total of 1430 cases.

63.64%, control group (rt-PA) incidence of 59.32%, real RR= 1.073, the sample size was calculated by PASS software to be 614 cases in each group; considering a dropout rate of 10%, the sample size was determined as 1364 (682 cases in each group). When the RR value was rounded to 1.07, the sample size was calculated to be 642 cases in each group; considering a dropout rate of 10%, the sample size was determined as 715 cases in each group and the total sample size is estimated to be 1430 cases.

#### 10. Premature Withdrawal and Missing Data

#### 10. Premature Withdrawal and Missing Data

In efficacy evaluation using the FAS population, missing data of efficacy endpoints will be carried forward (LOCF) using the last observed data after administration. Safety missing data will not be filled.

Missing data will not be imputed in the main analysis. ... In sensitivity analysis, multiple imputation was performed to impute the missing data of the primary efficacy outcome.

#### 13. Safety Analyses

#### 13. Safety Analyses

For most bleeding events, the number of bleeding events occurring over the treatment period will be summarized and Chi-squared test or Fisher's Exact test will be used to compare the number of bleeding events between treatment groups.

For most bleeding events, the number of bleeding events occurring over the treatment period will be summarized and Chi-squared test or Fisher's Exact test will be used to compare the number of bleeding events between treatment groups. This will also be tested by logistic regression model. The odds ratio with 95% CI will be reported.
